Hypotheses: We hypothesize that the DPR group will have a more benign hospital course as measured by time to full enteral feeds of 100 kcal/kg/day. We will also assess time to abdominal wall closure, time on TPN, length of hospital stay and intestinal motility post-closure using bedside ultrasounds. Secondly, we hypothesize that there will be no deleterious effects related to introducing the peritoneal dialysis solution into the silo.

Study Objectives

Primary Objectives:

1. To demonstrate that subjects treated with DPR will have a more benign hospital course as measured by time to full enteral feeds. The primary outcome measure will be time to full feeds of 100 kcal/kg/day. Secondary outcomes will include length of time until abdominal wall closure, time on TPN, time to intestinal motility, and total days in the hospital.
2. To demonstrate that the use of DPR in neonates with gastroschisis treated with staged silo closure will result in no significant changes in commonly measured clinical and laboratory safety parameters. This will be measured with more frequent clinical and laboratory assessments for the DPR group. Vital signs and strict intake and output will be monitored every 6 hours for 48 hours after the maximum dialysate infusion volume has been reached, then every 12 hours. Sodium, potassium, blood glucose and lactate levels will be monitored every 6 hours via heelstick, central/arterial line or venipuncture

Title: Direct Peritoneal Resuscitation in Gastroschisis

PI: [name]

Sponsor: UAMS

per NICU standard practice for 24 hours after the maximum dialysate infusion volume has been reached, then every 12 hours through Post-Closure Day 1.

Investigational Product

Dianeal PD-2 1.5% is a sterile, nonpyrogenic, hypertonic peritoneal dialysis solution containing dextrose, a monosaccharide, as the primary osmotic agent. Routine peritoneal dialysis in neonates and infants utilizes up to 40 mL/kg of dialysate per dwell. It will be administered via a 10 mm flat JP drain as a bolus infusion every 6 hours until the abdominal wall is closed (generally 3-5 days), but not to exceed 7 days maximum. The initial bolus infusion will be 10 mL/kg of Dianeal 1.5%. If tolerated, each subsequent infusion will be increased by 10 mL/kg of Dianeal 1.5% up to a goal infusion of 40 mL/kg (to a maximum volume of 100 mL) as tolerated.

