 - d. Dialysate will dwell for 1 hour after instillation of fluid. Any excess fluid will then be removed via JP drain.
2. Data for DPR
 - a. Blood samples will be obtained at the same time that routine laboratory values are performed. Supplementary research safety labs will require additional blood samples.
 - i. Complete CBC, sodium, potassium, bicarbonate/CO₂, chloride, BUN, creatinine, calcium, phosphate, albumin, glucose and magnesium
 - ii. Labs per standard of care are drawn each morning.
 - iii. Monitoring of additional labs will be per the discretion of the NICU team if necessary for pertinent patient care and monitoring.
 - iv. Heart rate, respiratory rate, blood pressure and pulse oximetry recordings will be recorded as part of the routine patient care. We will collect these measurements every 6 hours (\pm 30 minutes) at the time peritoneal fluid is infused.
 - b. Volume of fluid instillation and removal (date/time) will be documented in the medical record.
 - c. IV Fluids given

Title: Direct Peritoneal Resuscitation in Gastrochisis

PI: [name]

Sponsor: UAMS

Antibiotic regimen for both treatment groups

- 5 days of ampicillin and gentamicin will be given.
- No additional doses beyond 5 days unless clinically indicated.
- Ampicillin Sodium: Q8H, IV (100 mg/kg q8)
- Gentamicin Sulfate: Q24H, IV (4 mg/kg q24)

No additional antibiotics will be given as part of standard care. Post-surgical antibiotics will be administered at the discretion of the surgeon as required.

Standardized treatment algorithms

To minimize inter-subject management variation and bias in the interpretation of the results the following standardized criteria or algorithms are provided:

- i. Timing of abdominal closure/determination of readiness for closure
 - Serial reductions are performed with silastic silo placement for staged reduction using umbilical tape ties. The silo is assessed daily on morning rounds by the surgical team. Once the abdominal contents are at the level of the fascia, the abdomen is closed in the operating room. The average day to closure historically from CHND data is 5 days (Appendix C).
- ii. Initiation and advancement of enteral feeds

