 - Enteral feeding is begun after orogastric (OG) tube output has stopped and a bowel movement has occurred. OG tube output is checked at least every 4 hours (\pm 30 minutes) and/or before each feeding per NICU standard practice. Initiation of feeds is a clinical decision based on decreased gastric tube output, abdominal x-rays, and passing of stool. The initiation of enteral feeds is assessed daily on morning rounds by the neonatology team. Feedings start at an average of 7 days following abdominal wall closure. The advancement of enteral feeds will be based on standard practice at Arkansas Children's Hospital (Appendix D). Most feedings are started every six hours and advanced to every three hours as tolerated.
- iii. Tapering of parenteral nutrition
 - Tapering of the parenteral nutrition is congruent with the increase in enteral feeding, which is calculated based on the amount of nutrition and calories needed. The combination of parenteral nutrition and enteral feeding will be 100 kcal/kg/day. As the enteral feeding is increased, the TPN will be reduced proportionately. This is assessed once daily on morning rounds by the neonatology team.
- iv. Management of IVF/nutrition during DPR (i.e., changes in maintenance fluid or TPN rate during infusion)
 - The amount of IVFs is dependent on the subject's weight and calculated based on the volume of enteral feeds required to meet the subject's caloric needs. This is assessed daily on morning rounds by the neonatology team. IVF management changes will be made when clinically indicated by the neonatologists and guided by the subject's laboratory values. The current practice is not to replace the fluid lost during silo placement due to bowel edema often seen in these patients; thus, no additional changes are planned for the management of IVFs or nutrition during the intervention. The amount of dialysate fluid given will be documented in the medical record; it will dwell for 1 hour and then any remaining fluid will be removed.

Routine Laboratory Tests for both treatment groups

To reduce the risk of iatrogenic anemia and assure that excessive amounts of blood are not collected from any patient, the maximum allowable blood draw volumes are established per single phlebotomy collection. During routine daily lab draws, up to 1 mL of blood will be obtained for standard medical care.

Title: Direct Peritoneal Resuscitation in Gastroscisis

PI: [name]

Sponsor: UAMS

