Given the risk for fluid and electrolyte imbalances, close monitoring will be provided for the DPR group by using more frequent clinical and laboratory assessments in addition to standard NICU monitoring. Vital signs and strict intake and output will be monitored every 6 hrs for 48 hours after maximum dialysate infusion volume (100 mL) is reached, then every 12 hrs (\pm 30 minutes). Sodium, potassium, blood glucose and lactate levels will be monitored every 6 hours (\pm 30 minutes) via heelstick, central/arterial line or venipuncture per NICU standard practice for 24 hours after the maximum dialysate infusion volume is reached, then every 12 hrs (\pm 30 minutes) through Post-Closure Day 1.

Title: Direct Peritoneal Resuscitation in Gastroschisis

PI: [name]

Sponsor: UAMS

Subject will also be monitored for the following potential adverse events:

1. Hypokalemia: If the potassium falls to <3.0, additional potassium will be added to the IV fluid at the discretion of the treating and study physicians.
2. Lactic acidosis: Lactate levels will be monitored with laboratory checks at least every 12 hours during the treatment phase. Continued monitoring of lactic acidosis will include laboratory checks, fluid replacement, and stopping infusion of the dialysate fluid.
3. Hyperglycemia: During the first day (24 hrs) of treatment, blood glucose will be obtained within 1 hour prior to infusion and 1 hour (\pm 15 minutes) post-infusion in addition to routine daily assessments. The neonatologists will change IVFs to contain less dextrose as needed.
4. Hypovolemia: This will be treated with fluid replacement. Blood pressure monitoring and urine output assessment will guide management for amount of fluid replacement needed.
5. Peritonitis: This will be evaluated daily by examination of the effluent dialysate for any cloudiness. Cloudy fluid will be sent to the laboratory for cell count, gram stain, and culture. If the cell count is elevated, the subject will receive antibiotics as indicated. Subjects with confirmed peritonitis will be withdrawn from the study.
6. Definite (culture positive) sepsis: Neonates with active clinical sepsis will be excluded from the study by the hemodynamic parameter exclusion criteria (hypotension, hyper/hypoglycemia, lactic acidosis, etc.). During the dialysate infusion period, subjects who develop definite (culture positive) sepsis will be withdrawn from the study.

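### Objective 2 judges DPR on values the treating team may correct, while the corrections are only partly recorded across arms and are absent from the analysis

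*Combined protocol and SAP*

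**What the plan says.** Under Study Objectives, Primary Objective 2 is to show that DPR "will result in no significant changes in commonly measured clinical and laboratory safety parameters". On method it adds: "This will be measured with more frequent clinical and laboratory assessments for the DPR group".

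The parameters are also what clinicians act on:

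- Standardized treatment algorithms, item iv: "IVF management changes will be made when clinically indicated by the neonatologists and guided by" the infant's laboratory values. The next sentence, however, says "no additional changes are planned for the management of IVFs or nutrition during the intervention".
- Safety Monitoring, Hypokalemia: below 3.0, "additional potassium will be added to the IV fluid at the discretion of the treating and study physicians".
- Safety Monitoring, Hyperglycemia: "The neonatologists will change IVFs to contain less dextrose as needed".
- Safety Monitoring, Hypovolemia: treated with fluid, guided by blood pressure and urine output.

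On recording, "IV Fluids given" appears under Set-up for DPR, item 2 (Data for DPR), without composition. Data to be obtained lists NICU interventions (item 6), medications (12a) and hyperalimentation (12b) with no arm restriction.

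Data Analysis gives generic tests, which it introduces with demographic variables, and then the power statement for time to full feeds. It names no Objective 2 parameter, time point, margin or handling of corrective treatment.

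**The concern.** If DPR raises glucose, lowers potassium or shifts volume, and the team answers with less IV dextrose, more potassium or a bolus, the laboratory series returns towards normal. The trace of the DPR effect then lies in the fluid orders. An analysis that looks only at the values can report little change when the infants needed different treatment to stay there.

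At stake is how a primary safety objective is read. No difference in values under equal corrective input supports tolerability. No difference in values under unequal input is a different finding. As written, the plan does not let the reader tell the two apart.

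**Working it through.** **1. The plan's own figure.** None exists for Objective 2. The only power statement is for time to full feeds (20 per arm, 6-day difference, SD 7, two-sided 5%, at least 80%). The noncentrality is 6 / (7 × √(2/20)) = 2.71 on 38 df, which gives 75.2%. That shortfall is a separate matter, and nothing below depends on it.

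**2. Where a correction would leave a record.**

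- *IV fluids given:* listed for DPR only, without dextrose or potassium content.
- *Intake/output:* the Calendar and Schedule of Procedures carry no arm label, while Objective 2 and Safety Monitoring describe it as closer DPR monitoring. It gives volume, not composition.
- *Interventions, medications, hyperalimentation:* no arm limit, but composition is not specified.
- *Adverse events:* a laboratory abnormality that needs treatment counts as an AE, and all subjects are monitored. Recording starts with study drug, which SoC infants never receive, and no AE comparison is tied to Objective 2.
- *Individual discontinuation limits:* these concern stopping study drug and capture only marked drift, such as glucose above 250 for more than 12 hours.
- *Glucose before and after infusion:* DPR only, first 24 hours only.

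Corrections are thus partly visible, but no item gives dextrose, potassium and bolus input in both arms.

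**3. Sampling.** Under Research Laboratory Tests, DPR infants have sodium, potassium, glucose and lactate every 6 hours for 24 hours after maximum volume, then every 12 hours through Post-Closure Day 1. SoC infants have research lactate every 24 hours, with sodium, potassium and glucose from the daily routine panel. Drift can be seen, and acted on, sooner in DPR.

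**4. Glucose load that could be offset.** Appendix A gives 15 g/L. The goal bolus is 40 mL/kg every 6 hours, capped at 100 mL, so the cap binds above 100/40 = 2.5 kg.

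- Per dwell: 15 × 0.040 = 0.6 g/kg.
- Per day at goal: 0.6 × 4 = 2.4 g/kg instilled.
- As a rate if fully absorbed: 2,400 / 1,440 = 1.67 mg/kg/min.
- For an assumed 25–100% absorbed: 0.6–2.4 g/kg/day, or 0.4–1.7 mg/kg/min.

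The documents give no absorbed share. Since excess fluid is removed after a one-hour dwell, the top of the range is a ceiling.

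**5. Illustration of masking.** Assume a two-sample t-test with 20 per arm, SD 30 mg/dL, true rise δ, and a fraction f offset by treatment. Noncentrality = δ(1 − f) / (30 × √(2/20)) on 38 df. For δ = 25 and f = 0 this is 2.64, giving 72.8% power.

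| True rise (mg/dL) | f = 0 | f = 50% | f = 75% |
|---|---|---|---|
| 20 | 53.8% | 17.7% | 8.1% |
| 25 | 72.8% | 25.0% | 9.8% |
| 30 | 86.9% | 33.8% | 12.0% |

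In SD units, the difference detectable with 80% power is 0.91 SD. A 1.0 SD effect is missed 13%, 66% and 88% of the time at f = 0, 50% and 75%. A 1.5 SD effect is missed 0.4%, 36% and 79% of the time. The test, SD, effect sizes and offsets are all assumed.

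**The case against.** Safety under usual NICU care is a legitimate question, and values observed with the team free to respond answer it. Most corrections named in Safety Monitoring are tied to abnormal states, so many would surface as treated-abnormality AEs. Adjustment before a value becomes abnormal is possible under item iv, but no passage describes it. The day-1 glucose pairs are also informative: with steps of 10, 20, 30 and 40 mL/kg at 0, 6, 12 and 18 hours, the goal volume, if tolerated, is reached inside the 24-hour window. Each pair spans about two hours, while IV fluids are assessed daily on rounds. All of this stands and limits the concern. It does not supply a two-arm record of corrective input, or an analysis that uses one.

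A reader might infer more than the documents support:

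- *That corrections cannot be compared with SoC at all.* Several data items are not limited by arm, and intake/output may well be recorded in both.
- *That IV-fluid composition is collected for DPR and withheld for SoC.* The DPR-only item is fluids given. Composition is specified for neither arm.
- *That the comparison is biased towards safety.* Correction pulls mean differences towards zero, but more frequent DPR sampling can also find more abnormal values there. The net direction is not established, and the plan specifies no Objective 2 comparison to be biased.

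**Conclusion.** The point holds as a gap in recording and reporting. Objective 2 rests on values that the treating team may correct at its discretion. Those corrections are outside both the Objective 2 measure and Data Analysis, and the listed data capture them only in part. A null difference in raw values may therefore partly reflect correction.

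How much is unknown. The glucose load shows that the quantity is of a kind IV dextrose changes could offset. The power table shows only that a partly offset effect is harder to detect with 20 per arm. Neither estimates what will happen in this trial. This is a cheap improvement, not a flaw that invalidates the design.

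**What to change.** 1. **Record in both arms.** Extend the IV-fluid item under Data for DPR to SoC infants. From existing orders, abstract daily IV/TPN dextrose load, potassium added and fluid boluses, from silo placement to Post-Closure Day 1.
2. **Report side by side.** In Data Analysis, give for Objective 2 the arm difference with a 95% confidence interval in (a) the daily routine laboratory values common to both arms and (b) each corrective input: dextrose load, potassium and bolus volume. State that raw values are values under correction.
3. **Keep any composite supplementary.** An abnormal-or-corrected score should cover only parameters with a numerical limit in the Eligibility Criteria, which excludes fluid boluses. Its caveats should say that decisions are open-label and that DPR-only sampling every 6–12 hours raises both detection and correction in that arm.
4. **Reconcile the text.** Item iv of the treatment algorithms says no additional IV-fluid or nutrition changes are planned during the intervention, while Safety Monitoring describes IV-fluid changes. The sponsor should make the two consistent.

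The cost is chart abstraction for 40 infants and one analysis paragraph. Items 1 to 3 change no infant's care.

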- Liver function test abnormalities defined as AST > 200 , ALT > 200 , GGT > 100 [19]
- Electrolyte abnormalities, defined as:
 - Sodium < 130 or $> 150 \text{ mEq/L}$
 - Potassium < 3.0 or $> 6.5 \text{ mEq/L}$
- Hyperglycemia ($> 150 \text{ mg/dL}$) or hypoglycemia ($< 40 \text{ mg/dL}$)

Note: Potentially eligible subjects may be randomized and the silo placed according to the assigned study arm before all laboratory results are available. Laboratory values will be verified for eligibility prior to administration of DPR. Any ineligible subjects will be withdrawn from the study and may be replaced.

Randomization

The randomization schedule will be generated by the biostatistics department and the Principal Investigator (PI) will maintain a randomization log listing the subjects' ID and study arm assignment. Subjects will be randomized to either the DPR group or SoC group. If the subject is assigned to receive DPR, the ACRI Research Pharmacist will dispense the 1.5% Dianeal solution. The PI will calculate the dose to be distributed based on the subject's weight at the time of enrollment and administer the appropriate volume of 1.5% Dianeal solution as per instructions in the *Investigational Product* section.

Study Design and Procedures

This is a prospective double-arm study designed to evaluate the tolerability of direct peritoneal resuscitation (DPR) in neonates with gastroschisis. The experimental arm (DPR group) will receive adjuvant DPR with standard treatment for gastroschisis (staged silo closure). The control arm (SoC group) will receive standard treatment for gastroschisis only. All subjects will be placed in a silo shortly after birth and within 2 hours of admission to the NICU and subsequently serially reduced in silo with umbilical tape until the bowel contents are at the level of fascia and deemed suitable for closure.

A. SoC Group

[figure not shown]
The SoC group will be placed in silo within 2 hours of admission to the NICU per standard practice. These subjects will have no change in current clinical management by the neonatologists or pediatric surgeons and will not receive peritoneal dialysis fluid.

B. DPR Group

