All other standard care laboratory tests will be performed at the discretion of treating neonatologists.

Routine daily labs for gastroscisis patients include:

- Complete Blood Count (CBC) with differential
- Magnesium
- Renal function panel (sodium, potassium, chloride, bicarbonate/CO₂, BUN, creatinine, calcium, phosphate, albumin, glucose)

Research Laboratory Tests

Additional research labs for safety monitoring will be drawn via heelstick, central/arterial line or venipuncture per NICU standard practice. The first capture of research labs should coincide with routine labs to avoid repeat blood draws. Up to 2 mL of blood for research may be drawn each day in addition to the routine daily labs.

SoC Group

A research lab for lactate only will be drawn every 24 hrs (\pm 30 minutes) through Post-Closure Day 1.

DPR Group

Additional research labs will be drawn every 6 hrs (\pm 30 minutes) for 24 hours after the maximum dialysate infusion volume is reached, then every 12 hrs (\pm 30 minutes) through Post-Closure Day 1.

Research labs include:

- Lactate
- Sodium
- Potassium
- Glucose

Glucose via heelstick, central/arterial line or venipuncture per NICU standard practice will also be obtained within 1 hour prior to infusion and 1 hour (\pm 15 minutes) post-infusion for the first day of treatment.

The total amount of blood to be withdrawn per day, accounting for the additional research labs above for safety monitoring, will be up to 3 mL.

Ultrasound

We will perform trans-abdominal ultrasound imaging on all enrolled subjects from the time of abdominal wall closure until feedings have commenced. Additional imaging will be performed if the neonatology team has warranted a stop to feeding the neonate. This noninvasive modality will be used to determine categorization of intestinal motility. Abdominal ultrasound will be performed each morning at the bedside by the PI or other trained study personnel.

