We will document the presence of intestinal motility with continuous recording of ultrasound in all four quadrants for 30 seconds. Clips will be stored from each abdominal quadrant with the linear probe. If bowel motility is not recognized by 3 weeks post-operative, then the imaging will be terminated. A separate computer workstation connected to the image server will be used for image viewing and data analysis. Images and videos will be reviewed for quality and assessment of motility. To assess motility, the investigators will identify all distinct bowel loops visualized in the video clips and count movements in each of the bowel loops identified in the clip to determine a motility count for each quadrant. Videos will be classified as poor, fair or good. Motility will be quantified as the total number of distinct peristaltic movements visualized in each abdominal quadrant over 30 seconds. Cumulative motility (CM) will be

Title: Direct Peritoneal Resuscitation in Gastrochisis

PI: [name]

Sponsor: UAMS

calculated as the sum of motility from all four abdominal quadrants. Mean motility (MM) will be calculated as the mean number of distinct peristaltic movements per patient on each day of life imaged. A global descriptive score of bowel activity will also be assigned for each quadrant with the following categories: no, low, normal, or hyperactive peristalsis [20].

Data to be obtained (No. 1-13 are already obtained and available as part of the neonates' medical records):

All data collected as recorded by the NICU for the Children's Hospital Network Database (CHND) will be reviewed for the research. Data with an asterisks () are not included in the standard CHND database.*

1. Demographics
 - a. MRN, admit date, birth date, re-admission, gender, mother's zip code, birth weight, admit weight, gestation, birth head circumference
2. Transport and admission
 - a. Referral source
 - b. Morbidities and diagnoses present at admission
 - c. Lines, tubes, and drains present at admission
3. Maternal, prenatal, perinatal (This is part of the neonates' medical record and will be abstracted from the neonates chart.)

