Clinical site monitoring will be conducted by the UAMS Office of Research Regulatory Affairs (ORRA) to ensure that the rights and well-being of trial participants are protected; that the reported trial data are accurate, complete, and verifiable; and that the conduct of the trial is in compliance with the currently approved protocol/amendment(s), ICH GCP, and applicable regulatory requirements.

Monitoring specialists from ORRA will conduct periodic on-site, comprehensive monitoring as determined by a protocol-specific monitoring plan, which will be provided by the ORRA Monitoring Unit.

Data Handling and Recordkeeping

The Principal Investigator will carefully monitor study procedures to protect the safety of research subjects, the quality of the data and the integrity of the study. All study subject material will be assigned a unique identifying code or number. The key to the code will be kept in a file on a password-protected computer in the principal investigator's locked office. The data files will be kept in a separate file on the password-protected computer in the principal investigator's locked office. The only individuals who will have access to the code and information that identifies the subject in this study will be limited to investigators on this study. All data will be de-identified after analysis is complete by destroying the code key. De-identified data will be maintained as per UAMS and ACRI policy (currently all data will be kept until the last subject is 21 years of age plus 2 years) and destroyed per institutional guidelines.

All ultrasound studies will be transferred and stored on a secure image server located in the PI's office. The studies will be labeled prior to performing the study with a coded identification number based on the patients MRN. A separate computer workstation connected to the image server will be used for image viewing and data analysis. The ultrasounds will be reviewed on this separate password-protected computer only viewed by study personnel. All data will be de-identified after analysis is complete by destroying the code key. De-identified data will be maintained as per UAMS policy (currently seven years after publication) and destroyed per institutional guidelines.

Data Analysis

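### No masking is specified for scoring the motility clips, and the PI, who knows each infant's arm, may be a scorer

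*Combined protocol and SAP*

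**What the plan says.** **The outcome.** Study Objectives lists time to intestinal motility among the secondary outcomes. The Hypothesis section adds motility after closure, assessed by bedside ultrasound. The list of data to be obtained includes cumulative and mean motility.

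**Acquisition (Ultrasound section).** "Abdominal ultrasound will be performed each morning at the bedside by the PI or other trained study personnel". Imaging starts once the abdominal wall is closed.

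**Storage and viewing (Ultrasound section).** "Clips will be stored from each abdominal quadrant with the linear probe". "A separate computer workstation connected to the image server will be used for image viewing and data analysis".

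**Scoring (Ultrasound section).** For the count, "the investigators will identify all distinct bowel loops visualized in the video clips and count movements in each of the bowel loops". Video quality is put into one of three classes. "A global descriptive score of bowel activity will also be assigned for each quadrant", on four levels running from none to hyperactive. The person who assigns the grade is not named.

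**Who knows the arm (Randomization; Study Design and Procedures).** The PI keeps the log of arm assignments, works out the dose, and is to "administer the appropriate volume of 1.5% Dianeal solution". The SoC group receives no dialysate, and no sham is described.

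**Labels and access (Data Handling and Recordkeeping).** "The studies will be labeled prior to performing the study with a coded identification number based on the patients MRN". "The ultrasounds will be reviewed on this separate password-protected computer only viewed by study personnel". Access to the key that identifies infants is limited to the study's investigators.

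No section provides for masked, blinded or independent reading of the clips.

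**The concern.** Deciding which loops are distinct, what counts as a peristaltic movement and which of four grades a quadrant deserves are all judgements. The hypothesis has a direction: DPR should give the easier course. If the person making these calls belongs to the team that gives DPR and knows who received it, small and unintended leniency in one direction can produce a difference between arms where none exists. It can also enlarge a real one.

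Bias of this kind cannot be removed at analysis, because the scores carry no trace of it. Treatment in this trial would be hard to mask. Reading the clips is a different matter, because they are stored and viewed away from the bedside. The plan leaves unprotected an outcome that it could protect at little cost.

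**Working it through.** The plan gives no figure for motility: no reader agreement, no expected difference and no standard deviation. Its only sample-size statement concerns time to full enteral feeds and does not bear on this point. The check is therefore mainly a comparison of sections.

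1. **Is scoring a judgement?** Yes. The Ultrasound section asks for loops to be identified, movements counted, video quality classed and activity graded. It sets no threshold for saying that motility has returned.
2. **Who scores?** The investigators do the counting. The scorer of the grade is not named, but Data Handling and Recordkeeping restricts viewing to study personnel.
3. **Does a possible scorer know the arm?** For the PI this is certain, from the log and from giving the dialysate. For other investigators it is likely, since they may use the identity key and treatment is open. For other trained study personnel the documents are silent.
4. **Does the label mask the arm?** The label is a code based on the medical record number, and its stated purpose is confidentiality. The arm is not said to be in it. However, the people who count are in the role that may open the key, and nothing prevents a reader from knowing which infant is on screen.
5. **Could the clips be read masked?** Yes. They are stored by quadrant and viewed on a separate workstation. DPR runs only until closure and imaging starts at closure, so a clip need not show the arm. That residual fluid or other signs would not give it away is an assumption.
6. **Does the primary endpoint depend on the clips?** No. Under the standardized treatment algorithms, the neonatology team decides when to start feeds from gastric tube output, x-rays and stool. Ultrasound is not among the listed criteria.

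**Illustration of scale (assumed bias, not from the documents).** Suppose there is no true effect, n = 20 per arm, and the two-sample t-test at two-sided 5% that Data Analysis names for continuous data. Let knowledge of arm shift the mean score of one arm by b standard deviations. The test statistic then follows a noncentral t distribution with 2 × 20 − 2 = 38 degrees of freedom and noncentrality b × √(20/2) = b × √10. The false-positive rate is the probability that this statistic falls outside ± the 97.5th percentile of the central t on 38 degrees of freedom.

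| Assumed shift b (SD) | Noncentrality b × √10 | False-positive rate |
|---|---|---|
| 0 | 0 | 5.0% |
| 0.1 | 0.32 | 6.1% |
| 0.2 | 0.63 | 9.5% |
| 0.3 | 0.95 | 15.2% |
| 0.5 | 1.58 | 33.8% |

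The table shows how sensitive the test would be to a given bias. It does not estimate the bias in this trial.

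**The case against.** The strongest reply has four parts.

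**Only the PI's knowledge of arm is established.** This stands. A reader might infer that every scorer knows the arm. The documents do not say so: other trained personnel might not know, and the clips carry a code. What can be said is that masking is not specified and that one possible scorer certainly knows.

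**The listed outcome is a time to motility.** Whether motility is present is a coarser judgement than a count or a four-level grade, and the four-level grade is not in the list of data to be obtained. This stands in part. How counts become a time is not defined, so the path from a biased count to a biased time cannot be traced. But cumulative and mean motility are listed data built from the counts, and the first positive call is itself a reader's decision.

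**Masked reading is only a partial remedy.** This also stands. The operator at the bedside still chooses what is recorded. The rule that ends imaging at three weeks if motility has not been seen needs a timely read, which batch scoring cannot supply.

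**The stakes are limited.** Motility is a secondary outcome, and neither the primary endpoint nor the sample size rests on it. This is correct and limits how serious the point is. It does not remove the gap.

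**Conclusion.** The point holds as a gap in the plan: a named secondary outcome rests on subjective scoring, no masking of that scoring is specified, and the PI, who knows the arm, may be among the scorers. The size of any bias cannot be derived from the documents. The illustrated rates depend wholly on the assumed shift, on 20 infants per arm being analysed and on a t-test being used.

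Three stronger readings are tempting but unsupported. A reader might infer that the primary endpoint is contaminated, but time to full feeds is not derived from the clips. A reader might treat motility as the trial's only mechanistic outcome; the documents do not describe it so, their rationale turns on intestinal blood flow and ischemia, and lactate is measured in both arms. A reader might also assume that masked reading needs no staff time at all. The documents say nothing about reader numbers or workload, so the claim should stop at this: the existing trained readers can do it, with some added data handling.

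This is a worthwhile improvement that should be made, but it is not a flaw that undermines the trial's main result.

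**What to change.** State in the Ultrasound section that motility is scored masked to arm, as follows.

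- Someone who does not score, for example in the biostatistics department that generates the randomization schedule, re-labels each stored clip with a random code. The code is not based on the medical record number and is not linked to arm, infant or post-closure day. The scorers do not hold its key.
- The existing trained readers count and grade the re-labelled clips in batches and in random order. Where available, readers who neither dosed nor scanned that infant are preferred.
- Scores are locked before they are linked to arm.
- The masked score is the outcome of record. The bedside read is kept only for operational decisions such as the three-week imaging stop.

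Optionally, reading a sample of clips twice would supply the reader-agreement figure that the plan lacks.

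**Cost.** Re-labelling and shuffling add a little data handling, and scores become available later than the bedside scan. Sample size, visits and procedures on the infants do not change. Bedside acquisition remains unmasked, and the report should say so.
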